Dysphagia is a disabling, life-threatening symptom that can cause death in Multiple Sclerosis people (pwMS) through aspiration pneumonia. Speech therapists use behavioural therapies (compensatory and rehabilitative) to alleviate such swallowing problems, with limited benefit. Compensatory strategies such as postural changes and changes in food consistency, have been found to be partially effective, especially in patients with mild dysphagia and may be ineffective in patients with more severe dysphagia. The rehabilitative strategies include "no swallow exercises" which aim to strengthen isolated muscles used in swallowing (such as tongue strengthening) and "swallowing exercises" that aim at strengthening all the muscles used in swallowing while executing a hard, effortful, or prolonged swallow. To date, no randomized clinical trials have shown that rehabilitative strategies are effective. Neuromuscular electrical stimulation (NMES), often referred to as electrical stimulation, was introduced as a novel therapy for dysphagia in the late 2001 (Fred) The principles of NMES in the limb rehabilitation literature are well established. However published protocols applying NMES to swallowing function have shown mixed results in people with stroke and only one study was published on MS people. This will be a double blinded, randomized clinical trial (patients and research staff blinded) with two arms: standard speech therapy plus Active NMES vs speech therapy with Sham NMES. The aim of this study is to determine whether NMES added benefit to a therapy program comprised of standard swallowing exercises in dysphagic pwMS.

Introduction

Recent studies has shown that dysphagia in MS is more frequent than previously believed, the real prevalence ranging from 33 to 43%. (Solaro et al 2013) Dysphagia is a disabling, life-threatening symptom that can cause death in MS people through aspiration pneumonia. Dysphagia has also been reported in about 17% of patients with low disability (EDSS score lower than 2.5) (Abraham, et al 1997). These figures, which are based on

clinical evaluations, are undoubtedly higher when the symptom is evaluated by means of instrumental investigations (Tassorelli, et al 2008). According to the De Pauw study (De Paw, et al 2002), permanent dysphagia emerges in mildly impaired patients (EDSS 2-3), and becomes increasingly common as disability worsens, reaching a prevalence of 65% in the most severely disabled subjects (EDSS 8-9). Thus, diagnosis in the early stages may play an important role in limiting the consequences of this dysfunction. However, as patients themselves sometimes underestimate this symptom, diagnosis must be supported, as recently described in the literature, by functional tests and instrumental evaluations. A specific questionnaire (DYMUS: Dysphagia in Multiple Sclerosis) was published and validated for the assessment of dysphagia in MS. Its good internal consistency and the feasibility of administration has made it a reliable means to detect dysphagia in MS. In particular it consents to distinguish dysphagia to solids from dysphagia to liquids (Bergamaschi, et al.). 2008). However, a more detailed and objective evaluation is needed to investigate specific deficits and to plan appropriate rehabilitation; the Fiberoptic Endoscopy Evaluation of Swallowing (FEES) may be used for this purpose. In the 20 years since these initial reports, the FEES has become a validated technique for the evaluation of pharyngeal swallowing (Leder, et al 2008). The swallowing disturbances in MS are characterised by impairment of the oral and pharyngeal phases. Abraham et al. found impairment of the upper oesophageal sphincter in 100% of a small MS population (Abraham et al. 1997). Calcagno et al., using a mixed clinical and instrumental examination, subdivided their population into three groups according to the severity of dysphagia: severe, moderate and slight. Severe dysphagia group showed impairment of both oral and pharyngeal phases of swallowing, moderate dysphagia group showed motor impairment of the tongue, lips, velum or larynx, while the mild dysphagia group showed deficiency either of the velum or of the glottic closure. In the same paper, Calcagno et al. found that the compensatory strategies resolved dysphagia in about 94% of the cases (46 pts. Out of 49) (Calcagno et al., 2009). These strategies help to redirect and improve the food flow, avoiding aspiration and reducing the risk of pneumonia, but patients remain dysphagic and always need to perform compensatory strategies. (De Angelis et al 2008; Inagaki et al 2009,) As far as we know, this is the only study evaluating the rehabilitative approach, but it was not a control study. The role of food was highlighted in a recent paper showing that the main effect of food hardness is a delay in oral ejection time, which strongly delays total swallowing time, whereas pharyngeal bolus transit is dependent on its viscosity (Taniguchi et al 2008,). Recently, a pilot study (Frost, et al 2018) has shown as NMES could probably improve voice quality in MS patients: in fact, dysarthria has been proven to affect quality of life in MS patients (Piacentini, 2014).

NMES is a form of muscle stimulation with short electrical pulses that is frequently used in physiotherapy to strengthen healthy muscles and has been well described for several decades. NMES is used with a variety of different parameters for different types of treatment, since muscle contraction depends on different electrical parameters. An increase in frequency will result in an increased tension of the stimulated muscle, whereas increased intensity spreads current over a larger area, stimulating more motor units. Lastly, increasing the current duration causes more motor unit activation. NMES can be used for either muscle strengthening, retardation of atrophy or muscle re-education, and different stimulation parameters have to be chosen for each of these three

applications of NMES. The use of NMES in dysphagia treatment is relatively new; the first study was published in 2001 (Freed, 2001). Although Logemann reported that the therapeutic effects of NMES still lacks convincing supporting evidence, (Logemann, et al 2007), several studies have been carried out (Heijnen et al 2012, Kim et al 2017, Li et al 2015, Langmore et al 2016, Shaw et al 2007). Research using NMES, including randomized controlled trials, has demonstrated functionally improved swallowing with subjects moving from modified diets to more normal diet and fluids when NMES is used in conjunction with traditional therapy, but not when used in isolation (Chen, et al 2016). Moreover, recent UK guidelines from the National Institute of Clinical Excellence (NICE) recognized the positive results from these trials and promoted a further research to support the routine clinical use (NICE, 2014). NMES has been used in a wide range of patients, suffering from diverse pathologies: from head and neck cancer, to post-stroke dysphagia, obtaining different results (Chen 2016; Frost, 2018). Although it has been hypothesized, that neuromuscular electrical stimulation might enhance muscle strength in weak and disused oro-pharyngeal muscles, its clinical effectiveness remains unclear. Regardless the mechanism of action, clinical results showed that NMES enhances laryngeal elevation (Park et al 2009), reduces upper esophageal sphincter pressure (Heck et al 2012) and it enhances tongue base retraction during swallowing in health volunteers (Jungheim et al 2017). As reported by Oh (Oh et al 2007) and Hamdy (Hamdy et al 2000), the improvement of the swallowing function in stroke, after electrical stimulation is correlated with cortical reorganization, suggesting that multiple sessions of NEMS of the neck muscles could improve swallowing function also through the recruitment of new cortical areas.

NMES has been used in treating dysphagia in MS patients (Alali, 2016). A pilot study performed with pharyngeal electrical stimulation for dysphagia associated with MS showed an improvement in penetration and aspiration scale, suggesting a potential benefit for the treatment of this symptom (Restivo et al 2013)

However, this type of treatment can be performed only in specialized centers and it is probably more invasive than NMES. In 2009, Bogaardt (Bogaardt et al 2009) conducted a Class IV trial with a sample of 25 patients with MS. The primary focus of the study was to examine the effects of NMES on pooling of saliva or liquid in the valleculae and pyriform sinuses. Six of the 25 patients had significant reduction in pooling of saliva in the pyriform sinuses, and 23 participants reported through a questionnaire that their swallowing had improved (Bogaardt, et al 2009). As far as we know, this is the unique paper focusing on the therapeutic effects of NMES in MS patients. Our research group recently published about the use of NMES in people with stroke and dysphagia. The methodology resulted safe with a good effectiveness in addition with traditional speech therapy. In fact, combined treatment seem to reduce the risk of penetration and aspiration in stroke dysphagic people. (Simonelli et al 2019).

The aim of the study is to determine whether NMES added benefit to a therapy program comprised of standard swallowing exercises in dysphagic pwMS

Materials and methods

The research plan will be implemented within a multi-center collaboration. Each of the 8 centers will recruit 17 inpatient and outpatient with a diagnosis of MS, according to revised McDonald criteria (Thompson et al 2018), with dysphagia. Each patient will be evaluated with a general and neurological evaluation scored according to the Expanded Disability Status Scale (EDSS) of Kurtzke and its functional systems.

Inclusion criteria will be:

- 1) Sex (both);
- 2) Age (older than 18)
- 3) Diagnosis: definite MS (Thompson et al 2018)
- 4) Stability: recruited subjects must be in a stable phase of the disease, without relapses which induce worsening > 1 point in the EDSS and with an EDSS <=8
- 5) ASHA<6 and DYMUS >2
- 6) Novelty: subjects should not have been trained with dysphagia program in the last 6 month
- 7) Mini-Mental State Examination: > 24;

Exclusion criteria will be:

- 1) dysphagia related to other diseases
- 2) presence of tracheal cannula
- 3) local or general contraindications to the use of equipment for electrical muscle stimulation of the neck
- 4) malignancies or acute inflammation in the anterior region of the neck.
- 5) lack of collaboration due to mental impairment

Baseline characteristics:

At T0, a clinical and instrumental examination will be suggested, concerning:

- the cognitive profile (Brief International Cognitive Assessment for MS); (Benedict et al 2012)
- the presence and severity of fatigue scored with Modified Fatigue Impact Scale; (Tellez et al 2005)
- the presence and severity of depression (Beck depression Inventory); (Solaro et al 2016)
- the motor performance with Timed 25 Foot walk Test ,Timed Up and Go, and 9 hole Peg Test (Gijbels et al 2012, Kragt et al 2006, Sebastião et al 2016,);
- the body mass index (kg/m²) and blood parameters (in particular proteins and albumin) will be examined in all of the patients, in order to define their nutritional state;
- Mini Nutritional Assessment (Vellas et al , 2006). To verify the appropriate food calories intake
- the voice quality: (Frost, 2018). In order to carry out the speech analysis, the software PRAAT (a system for doing phonetics) was developed by Paul Boersma & David Weenink at the Phonetic Sciences department at the University of Amsterdam) will be adopted.

As far as the dysphagia concerned, its presence and severity will be assessed using:

- ASHA score, (American Speech –Language Hearing Association, 1998) performed by a speech therapist; ASHA suggests that patients should be divided in groups from level 1

(individuals cannot swallow anything safely by mouth) to level 7 (individual's ability to eat independently is not limited by swallowing function. Swallowing is safe and efficient for all food consistencies. Compensatory strategies are effectively used when needed).

A non instrumental evaluation will be used, due to its feasibility, by an examiner unaware of the research protocol. The assessment takes into consideration anamnesis regarding the swallowing problem, evaluation of the anatomy and functionality, of sensitivity and the reflexes, of the swallowing apparatus. Finally, the oral feeding test is performed, which evaluates the oral and pharyngeal phases of swallowing.

- FEES, performed by a phoniatrician in a blinded way in order to verify: 1) rest status, with reports of possible secretions or food presence, particularly in the lower pharyngeal tract; 2) preliminary report on: a) glottis enclosure ability (phonation) b) coordination between breathing and vocalization, c) ability and sensitivity of the cough reflex. 3) "dry" swallowing, with observation of the pushing-back movement of the tongue, the time for swallowing voluntary activation(pharyngeal phase), the research of larynx elevation and epiglottis basculatory movement; 4) proposal of food coloured with green of varying consistencies to test the swallowing act with determined quantities: a) liquid: a spoonful, i.e. 10 ml, repeated three times; b) semisolid (gelatine consistency): a spoonful, i.e. 10 ml, repeated three times; c) solid: half a cracker, repeated with three bits. During each swallowing act, the observer will have to examine the same functions described above in point n. 3, and his/her attention will focus on premature falls of the bolus towards the pharynx, with or without penetration and/or aspiration; the word "premature" indicates that it is contemporary to the oral phase and is to be used to indicate the alimentary falls before the pharyngeal phase of swallowing; penetration and/or aspiration during the pharyngeal phase of swallowing; laryngeal

penetration, defined as passage of material into the laryngeal vestibule above the vocal folds and aspiration, defined as passage of material under the level of the true vocal folds; reports of the permanence of food and/or secretion in the lower tract of the pharynx after the pharyngeal phase of swallowing (pharyngeal residue or pooling) and evidence of penetration and/or aspiration of this residual component; the occurrence, or absence, of the cough reflex as a consequence of penetration and/or aspiration.

According to the FEES examination will be scored the severity of dysphagia through the Dysphagia Outcome and Severity Scale (DOSS Score) (O'Neil et al 1999). We'll also use the Penetration and Aspiration Scale (Rosembek et al, 1996) and the Pooling scale, able to evaluate the excess residue in the pharynx and larynx. (Farneti et al 2014). The FEES will be record by video.

- the DYMUS questionnaire (Bergamaschi et al., 2008)
- the Swal-QOL. This is a 44-items questionnaire is a highly valid instrument for evaluating and has a very reliable shorten reproducibility (Ginocchio D et al 2016). Its 11 subscales represents the different aspects of quality of life. The minimum and maximum score per subscale ranges from 0 to 100, indicating extremely impaired quality of life versus no impairment experienced by the individual;

- Visual Analogue Scale (VAS) for dysphagia: self-assessment of dysphagia severity will be rated from 0 (none) to 10 (worst imaginable) scale. Respondents will be classified as having no dysphagia (score 0), mild dysphagia (scores 1-4), moderate dysphagia (scores 5-6) and severe dysphagia (scores 7-10);
- the meal time.
- CGI (Clinical Global Impression Scale) scale for evaluating clinical changes after treatment (Busner et al 2007)

Two Speech Language Pathologists (SLPs) trained in dysphagia management will be involved: one, as evaluating speech therapist, will be blind on the NMES treatment and the other one as a treating speech therapist.

As far as the dysphagia concerned, patients will be considered dysphagic according to ASHA (score<6) and DYMUS (score >2).

The NICE guidelines (NICE 2014) identified from the literature a number of possible adverse events for NMES, which they classified under Safety section.

Those deemed likely were burning sensation, skin irritation or soreness beneath the electrodes and coughing or expectoration, neck or jaw pain and increasing severity of dysphagia. Incidences of these events were recorded during the NMES therapy. The therapists who delivered the NMES therapy were also asked to record any other adverse reactions. In addition, therapists were asked to record whether the adverse reaction was resolved by repositioning the electrodes.

Finally, the speech and language therapists were asked to note whether there was any change in the quality of the voice as a result of the NMES, as previous research has shown (Frost, 2018).

The training will consist of 16 sessions. After 8 (T1) every patient will be examined using: ASHA scale; VAS for dysphagia and meal time. After 16 (T2) sessions, every patient will be examined with both clinical and instrumental examinations; after 12 weeks (T3) from the end of treatment every patient will undergo clinical evaluations. At T3 the CGI will also be submitted to the pwSM caregivers

Rehabilitation treatment

According to the presence of dysphagia, scored as previously described by ASHA and DYMUS scales, we estimate that, we can enrol 17 pwMS for each center.. The candidates will be randomly allocated (according to 2 blocked randomization lists, generated electronically by www.random.org) in two groups numbered consecutively and equal numbers will be allocated to the intervention group “standard rehabilitative treatment plus neuromuscular electrostimulation” (SRT-NMES), odd numbers to the control group “standard rehabilitative treatment plus Sham (SRT-S). Randomization will be done by single center.

Both SRT-NMES and SRT-S groups will be received 16 sessions of traditional dysphagia therapy according to their degree of dysphagia, contemporary associated with Sham or NMES, according to our previous experiences, two 30-min treatment a day, separated by a rest period of at least 45 minutes for four consecutive days per week, within a period of 4 weeks.

During the study period, steroids will not be permitted.

Patients who will experience relapses during the study period will be considered as drop-out.

Traditional dysphagia therapy

The training will be performed by expert speech therapists. Traditional dysphagia therapy (TDT) involved orofacial, lingual, and laryngeal motor exercises, including progressive resistance training, combination of lingual strengthening exercises, laryngeal adduction-elevation exercises, effortful swallow manoeuvre, Mendelsohn manoeuvre (Mendelsohn et al 1987), Masako manoeuvre (Fujii et al 1996) and Shaker exercises (Shaker et al 1997). Compensatory swallowing strategies included various modifications of head, neck, and body postures and adjustment of food/liquid temperature, viscosity, and volume. It may be necessary to whisk food completely or partially, often adding a thickening liquid in drinks to allow an adequate water intake for nutritional support.

(Gonzales-Fernandez et al 2008). The choice of specific positioning strategies and swallowing manoeuvres or exercises was based on the FEES findings and the clinical swallowing examination. The rehabilitative treatment will be administered in the 8 centers taking part to the study .

Neuromuscular electrostimulation (NMES)

In the present study, VitalStim equipment will be used (VitalStim Therapy; Chattanooga Group, Chattanooga, TN, USA). Therapists received additional training and information on NMES by an experienced laryngologist certified to use surface electrical stimulation. The training was given according to the manual of the manufacturer, the VitalStim certification course (<http://www.vitalstim.com>).

Skin preparation and electrode placement will be in accordance with the manufacturer's instructions.

Channel 1 is horizontally immediately above thyroid notch. Channel 2 is parallel, below notch.

Having applied the electrodes, the amplitude of each channel of the stimulator will be increased and the subject will identify when they will be able just feel it. The amplitude will be then further increased until the subject will feel a 'grabbing sensation' which corresponded to muscular contraction. This will be the amplitude used for the therapy. This process will be repeated for the second channel of the stimulator. The typical electrical stimulus is at 80 Hz and at 300 microsec, and it will be adapted to avoid annoying stimulus to the patients.

During therapy, both channels will be active. In "sham" group the same electrodes will be positioned.

To maintain the double-blind study, the electrodes in the "sham" group will be placed in the same positions as the active treatment, with a current between 3 and 5 mA (average of 3.5 mA) until the patient begins to feel a slight tingling, current unable to perform muscle contraction. (Park J. S. et Al).

During electrical stimulation, traditional swallowing therapy will be carried out, by a trained speech therapist.

Before the study starting, the team of the 8 Centres, reached a consensus for the administration of clinical scales and how to score the FEES findings.

Briefly:

Subjects:

136 clinically definite MS subjects, both outpatients and inpatients (see inclusion and exclusion criteria below). Each patient will be informed on overall requirements of the study, and his/her written consent will be obtained

Primary Outcome:

The first aim of this study is to determine whether NMES adds benefit to a speech therapy traditional program. Performance between the groups will be compared at completion of treatment, after adjustment for baseline differences.

The mean difference at ASHA score between SRT-S vs SRT-NMES will represent the primary outcome.

Secondary outcome will be the differences obtained at T0-T2 and T0-T3 in the two groups in DYMUS scale, FESS/DOSS score, the MNA, the Swallowing Quality of life questionnaire, Penetration and Aspiration Score, the Visual Analogue Scale and the Pooling score.

Hypothesizing a response to treatment in the 30% of the SHAM group and in 60% of active NMSE a sample size of 56 subjects for each group provides a power of 0.9 and a significance level of 5%. ($h = 0.6128748$, $n = 55.94774$, sig.level = 0.05, power = 0.9, alternative = two.sided)

We estimate we could have a dropout of approximately 10-15%. In this light we decided to enrol 136 pwMS (17 for each center) Baseline characteristics and comparability of the two treatment groups will be assessed by the two samples t-test for continuous variables and by chi-square or Fisher's exact test for categorical variables. To address the first aim of the study, will be used analysis of covariance comparing changes in study outcomes from baseline to T2 adjusting for differences in baseline measures of swallow performance, diet and quality of life across the two treatment arms. To evaluate the differences intra-group, we will performed longitudinal analyses using general linear models for repeated measures of outcome data collected at baseline to T2 .

Italian MS Society Research Foundation is funding the study

(Grant No 2019/R –Multi/ 005)

References

Alali D1, Ballard K2, Bogaardt H Treatment Effects for Dysphagia in Adults with Multiple Sclerosis: A Systematic Review. *Dysphagia*. 2016 Oct;31(5):610-8. doi: 10.1007/s00455-016-9738-2. Epub 2016 Aug 4.

American Speech-Language Hearing Association. National Outcomes Measurements System (NOMS): Adult Speech-Language Pathology Training Manual. Rockville, Md: American Speech-Language Hearing Association; 1998

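### The only limit on earlier treatment is a 6-month window for dysphagia training, so some patients with past surface neck NMES can enter and may recognise active or sham

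*Protocol*

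**What the plan says.** **Eligibility (Materials and methods).** Inclusion criterion 6 is "Novelty: subjects should not have been trained with dysphagia program in the last 6 month". The only criterion that mentions electrical stimulation is exclusion 3, "local or general contraindications to the use of equipment for electrical muscle stimulation of the neck". It concerns whether stimulation is safe for the patient, not whether the patient has had it before. Exclusion 1 removes dysphagia caused by other diseases.

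**Blinding (opening summary).** "This will be a double blinded, randomized clinical trial (patients and research staff blinded) with two arms".

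**What patients feel (Neuromuscular electrostimulation).** In the active arm, "The amplitude will be then further increased until the subject will feel a 'grabbing sensation' which corresponded to muscular contraction", and that amplitude is used for therapy. In the sham arm the electrodes sit in the same places and a current of 3 to 5 mA is applied "until the patient begins to feel a slight tingling, current unable to perform muscle contraction".

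**Outcomes.** The primary outcome is the mean difference in ASHA score. The secondary outcomes include DYMUS, the swallowing quality-of-life questionnaire and the VAS, alongside scores read from the endoscopy. The evaluating speech therapist is blind to the NMES treatment, and the endoscopy is done blind.

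**The concern.** The sham copies electrode position but not sensation. A naive patient has no reference for what active stimulation feels like; a patient who has had it does. Patient blinding therefore depends partly on patients not having met the active sensation before.

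Criterion 6 works as a washout for carry-over from training. A 6-month window is a reasonable tool for that purpose, but there is no reason to expect the memory of a muscle contraction in the neck to fade on the same schedule. The label of the criterion suggests that treatment-naive patients were wanted; its wording does not secure that.

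At stake is the credibility of outcomes that patients rate themselves. If those who recognise sham report less benefit and those who recognise active report more, the difference between arms is inflated, and a larger sample does not shrink that error. The baseline assessments listed do not include earlier neck stimulation, so on that list affected patients could not be picked out later.

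**Working it through.** **Step 1. Which earlier exposures do the criteria catch?**

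| Earlier exposure | Caught by | Can enter? |
|---|---|---|
| NMES within a dysphagia programme, last 6 months | Inclusion 6 | No |
| NMES within a dysphagia programme, more than 6 months ago | None | Yes |
| Surface neck NMES outside a dysphagia programme, e.g. for voice, at any time | None clearly | Yes |
| NMES for dysphagia due to another disease, that disease still the cause | Exclusion 1 | No |

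The gap is the second and third rows.

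**Step 2. Is such exposure possible in MS?** The Introduction says NMES has been used for dysphagia in MS, dates the first dysphagia study to 2001, and cites a pilot suggesting benefit for voice in MS. It also says the authors know of only one paper on the therapeutic effects of NMES in MS, with 25 patients. Exposure is possible and probably uncommon. No share is given.

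**Step 3. The plan's own figure.** The sample-size paragraph assumes response in 30% (sham) and 60% (active), two-sided 5%, power 0.9:

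- h = 2·asin(√0.6) − 2·asin(√0.3) = 0.61287
- n = 2·((1.960 + 1.282)/h)² = 55.95, so 56 per group

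This reproduces the stated h and the 56 per group. The point changes neither; 56 per group is used below only as a frame.

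**Step 4. Size on a self-rated scale (assumed inputs).** Let a share q recognise their allocation, and let recognition move the self-rating by s towards benefit in the active arm and by s away from it in the sham arm.

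- Bias in the arm difference = q·s − (−q·s) = 2qs
- q = 0.05, s = 1 VAS point: 2 × 0.05 × 1 = 0.10
- q = 0.10, s = 1 VAS point: 2 × 0.10 × 1 = 0.20

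The VAS runs from 0 to 10.

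**Step 5. Size as a false-positive rate (assumed inputs).** Take no true effect, 30% response in both arms and 56 per arm. A share f recognises the allocation, which shifts their response probability by b, up in active and down in sham.

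- p(sham) = 0.3 − fb, p(active) = 0.3 + fb, difference d = 2fb
- SE = √{[p(sham)(1 − p(sham)) + p(active)(1 − p(active))]/56}
- Rejection probability = Φ(d/SE − 1.96) + Φ(−d/SE − 1.96)

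For f = 0.10, b = 0.2: proportions 0.28 and 0.32, d = 0.04, SE = √[(0.2016 + 0.2176)/56] = 0.0865, d/SE = 0.462. The rate is Φ(−1.498) + Φ(−2.422) = 0.067 + 0.008 = 7.5%.

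| f | b | d | Two-sided false-positive rate |
|---|---|---|---|
| 5% | 0.1 | 0.01 | 5.2% |
| 5% | 0.2 | 0.02 | 5.6% |
| 10% | 0.2 | 0.04 | 7.5% |
| 20% | 0.2 | 0.08 | 15.3% |

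The values of q, s, f and b are not in the protocol. The table describes an outcome that responds to patient expectation; it is not an estimate for the ASHA score.

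**The case against.** The strongest reply is that exposed patients will be rare and the primary outcome is protected. Most of that stands. The ASHA score is rated by a speech therapist who is blind to treatment, the non-instrumental examiner is said not to know the research protocol, and the endoscopic scores are read blind. What remains for ASHA is indirect: the examination includes a history taken from the patient and a feeding test, so report, effort or an unguarded remark could still reach the rating. At 5% exposure the illustrative effect is slight.

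Three further replies also stand in part.

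- **Direction is assumed.** Anyone with past NMES who still meets the entry thresholds on ASHA and DYMUS is still dysphagic after it. Recognising the active current could lower that person's hopes. Bias in favour of NMES is the likelier direction, not a certain one.
- **Recognition is not certain.** The active stimulus is adjusted to each patient's comfort, so the sensation varies, and nothing in the protocol shows that a memory from years ago identifies it. Better placed to recognise is as far as the text goes.
- **The sensory difference exists for everyone.** Naive patients could also guess, particularly if told what to expect. The consent material is not available, so this cannot be judged here.

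A reader might infer that the group's own published NMES work makes previously stimulated candidates likely at these centres. That work was in stroke, this trial enrols definite MS, and exclusion 1 removes dysphagia from other diseases, so it does not support the inference. Nor does the text support adding pharyngeal stimulation to the gap: the protocol treats it as a different and probably more invasive technique, and nothing shows that it teaches the surface sensation.

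**Conclusion.** The point holds as a modest weakness in eligibility. The criteria admit patients with surface neck NMES more than 6 months ago, or outside a dysphagia programme, into a trial that claims patient blinding while setting the two arms to feel different. The outcomes mainly at risk are DYMUS, Swal-QOL and VAS; ASHA is less exposed.

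On assumed inputs the bias is 0.1–0.2 VAS point at 5–10% recognition. The false-positive rate for an expectation-sensitive outcome stays near 5% at 5% recognition and becomes a concern only at 10–20%, which nothing in the protocol suggests for MS. The effect is likely small.

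Two stronger conclusions are not supported. One is that anyone who has ever had neck NMES can enter: NMES given within a dysphagia programme in the last 6 months is caught by criterion 6. The other is that the primary comparison is biased in favour of NMES: its rater is blinded, and both the share exposed and the direction of any shift are unknown.

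**What to change.** Add one exclusion criterion: any previous surface neuromuscular electrical stimulation of the neck, for dysphagia or voice, at any time. Check it with one screening question. Keep the 6-month window for other dysphagia training, where it serves its purpose as a washout.

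The cost is one line, one question and the loss of a few candidates, probably very few if NMES in MS is as uncommon as the protocol implies. The sample size of 56 per group and the enrolment of 136 do not change. If the sponsor prefers not to exclude anyone, recording earlier neck stimulation at screening, and the patient's guess of allocation, would at least let its influence be examined.

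The change does not remove the risk that naive patients guess their allocation from the sensation, and it should not be presented as doing so.
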